2.8. Efficacy Evaluations

2.8.1. Continuous Glucose Monitoring

The last 2 days with at least 80% of expected measurements prior to dosing will be considered the run-in days for each of the parameters. The last 2 days with at least 80% of expected measurements prior to 8 hours after the last dose will be considered the on treatment days. The measurements more than 8 hours after the last dose will be considered the follow-up days.

The 24-hr period (6AM to 6AM), nighttime (from 10pm to 6am), daytime (6AM to 10PM), and post-prandial (first hour after meal start time including breakfast, lunch, and dinner) glucose values will be summarized. The mean, standard deviation, minimum, maximum, first quartile, median, third quartile and inner-quartile range will be presented.

The area under the curve (AUC) will be derived for each of the time periods (24-hour, daytime and nighttime) using the indicated days (run-in days, treatment days and follow-up days). The average glucose measurement will be derived by dividing the AUC by the number of observed hours. The average change from run-in will be derived for each treatment regimen for both the treatment days and the follow-up days.

The placebo adjusted change in means will be derived for each of the active therapy regimens by subtracting the placebo mean (the mean change from run-in while the subject was receiving placebo) from the active therapy mean (the mean change from run-in while the subject was receiving the active therapy).

The placebo adjusted change in means will be derived for both the treatment days and the follow-up days. The placebo adjusted change in means will be analyzed using an Analysis of Variance (ANOVA) with treatment as the main effect to determine whether multiple doses a day has an effect on the CGM parameters. If the residuals are not normally distributed, then a Kruskal-Wallis test (one-way analysis of variance on the ranks) will be performed.

The ratios of the placebo adjusted change in means between the active treatments within each subject will also be derived to estimate the magnitude of the dose response.

Summary statistics will be presented for both the placebo adjusted change in means and the ratios of the placebo adjusted change in means. Analysis results will be presented for the change in means.

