- ⁶A standardized breakfast will be provided on Day 1. Beginning with dinner on Day 2 and ending with breakfast on Day 10, breakfast and lunch will be provided no sooner than 45 minutes after corresponding treatment doses. Dinner will be provided at approximately 7pm (±60 minutes). Standardized snacks will be provided between breakfast and lunch, between lunch and dinner, and between dinner and bedtime.
- ⁷Blood samples (scheduled per randomization scheme) for insulin and C-peptide will be drawn pre-dose and every 30 minutes (± 5 minutes) postdose until 5 hours has elapsed.
- ⁸Randomization will occur on the morning of Period 1/Day 4. Crossover will occur on the morning of Period 2/Day 4 and then again on the morning of Period 3/Day 4.
- ⁹Subjects will receive their assigned randomized treatment from the morning of Day 4 through the evening of Day 8. Doses will be administered at approximately 7am (±60 minutes), 1pm (±60 minutes), and 10pm (±60 minutes).

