5.3.1.2 Double-Blind Treatment Administration

Study treatment (active or placebo) will be administered during Visit 2 on Days 4-8. **Prior to administering the scheduled dose of study drug, the most recent available reading on the CGM monitor must indicate a blood glucose of ≥ 70 mg/dL.** On all days, subjects will receive a dose of study treatment or placebo at approximately 7am (\pm 60 minutes), approximately 1pm (\pm 60 minutes), and a dose before bed at approximately 10 pm (\pm 60 minutes).

Subjects may be randomized to receive ORMD-0801 qd, bid, or tid:

- Subjects receiving ORMD-0801 qd will receive their dose at approximately 10pm (\pm 60 minutes), while receiving identical placebo at approximately 7am (\pm 60 minutes) and at approximately 1pm (\pm 60 minutes).
- Subjects receiving ORMD-0801 bid will receive their doses at approximately 7am (\pm 30 minutes) and before bed at approximately 10pm (\pm 60 minutes), while receiving placebo at approximately 1pm (\pm 60 minutes).
- Subjects receiving ORMD-0801 tid will receive their doses at approximately 7am (\pm 60 minutes), at approximately 1pm (\pm 60 minutes), and before bed at approximately 10pm (\pm 60 minutes).

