8.3 Continuous Glucose Monitor Evaluation

For the purpose of analysis:

- 24-hour will be considered to be from 6AM to 6AM,
- Daytime will be considered to be from 6AM to 10PM, and
- Nighttime will be considered to be from 10PM to 6AM.

The last 2 days with at least 80% of expected measurements prior to dosing will be considered the run-in days for each of the parameters. The last 2 days with at least 80% of expected measurements prior to 8 hours after the last dose will be considered the on treatment days. The measurements more than 8 hours after the last dose will be considered the follow-up days.

The area under the curve (AUC) will be derived for each of the time periods (24-hour, daytime and nighttime) using the indicated days (run-in days, treatment days and follow-up days). The average glucose measurement will be derived by dividing the AUC by the number of observed hours. The average change from run-in will be derived for each treatment regimen for both the treatment days and the follow-up days.

The placebo adjusted change in means will be derived for each of the active therapy regimens by subtracting the placebo mean (the mean change from run-in while the subject was receiving placebo) from the active therapy mean (the mean change from run-in while the subject was receiving the active therapy). The placebo adjusted change in means will be derived for both the treatment days and the follow-up days.

The placebo adjusted change in means will be analyzed using an Analysis of Variance (ANOVA) with treatment as the main effect to determine whether multiple doses a day has an effect on the CGM parameters.

The ratios of the placebo adjusted change in means between the active treatments within each subject will also be derived to estimate the magnitude of the dose response.

Summary statistics will be presented for both the placebo adjusted change in means and the ratios of the placebo adjusted change in means. Analysis results will be presented for the change in means.

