2.2. Study Populations

Safety population: All patients who receive at least one dose of the study drug will be included in the safety population

Efficacy population: Intent-to-treat (ITT) population with last observation carried forward (LOCF) in patients who receive at least one treatment with study drug and in whom CGM data was collected at least once during treatment.

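### The on-treatment CGM window has no earliest day and hangs on an undefined last dose, so run-in days can be counted as treatment

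*SAP*

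**What the plan says.** SAP 2.8.1 fixes three sets of CGM days, and Protocol 8.3 gives the same rules. Before treatment, "The last 2 days with at least 80% of expected measurements prior to dosing will be considered the run-in days". During treatment, "The last 2 days with at least 80% of expected measurements prior to 8 hours after the last dose will be considered" the on-treatment days. Afterwards, "The measurements more than 8 hours after the last dose will be considered the follow-up days". The 24-hour interval runs 6AM to 6AM, daytime 6AM to 10PM and night-time 10PM to 6AM.

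Three things are not stated: an earliest on-treatment day; whether the last dose is the last one taken or the last one scheduled; and whether the 80% is a share of the full interval or only of the part before the cut-off.

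The efficacy population in SAP 2.2 is defined "in patients who receive at least one treatment with study drug and in whom CGM data was collected at least once during treatment", so a single dose is enough to be included. SAP 2.13 allows no imputation beyond interpolation within the trapezoids.

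Randomised dosing runs from the morning of Day 4 to the evening of Day 8, at about 7am, 1pm and 10pm (Protocol 3.6). Protocol 5.3.1.2 adds that, before a scheduled dose, "the most recent available reading on the CGM monitor must indicate a blood glucose of ≥ 70 mg/dL". It does not say whether a dose held on this ground is skipped or delayed. The primary objective (SAP 1.3.1) and Table 14.2.1.1 name Day 8 as the end of treatment.

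**The concern.** The rule counts backwards from a point that moves with the subject's dosing, and nothing stops the count at Day 4. If a period ends early enough, the two most recent qualifying days lie before the first randomised dose. The change from run-in then compares run-in with itself, or with a mixture of run-in and treatment.

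The same movable end point can take Day 8 out of a period in which the subject stayed to the end with the monitor running. The event that would do this is a CGM reading below 70 mg/dL before the last dose, so the choice of days would depend on glucose, which is the outcome. The night after the hold would move into follow-up, which feeds the Day 9 secondary comparison.

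**Working it through.** **Inputs.** Dose times 7am, 1pm and 10pm, each ±60 minutes, on Days 4–8, which is 15 dose slots per period (Protocol 3.6). Cut-off = last dose + 8 h. A day qualifies at 80% coverage or more (SAP 2.8.1). Assumed: CGM recording without gaps from early on Day 1, *last dose* meaning the last dose taken, and 80% of the full interval.

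**Check at full dosing.** 10pm on Day 8 + 8 h = 6AM on Day 9, exactly the end of the 24-hour Day 8. Given at 9pm, the dose still leaves 23/24 = 95.8% of the day and 7/8 = 87.5% of the night. The rule returns Days 7–8 against run-in Days 2–3, so it works as intended when every dose is given.

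**24-hour parameter by last dose in the period.** D2, D3 and D4 are the mean glucose of those days.

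| Last dose | Cut-off | Coverage of that day | On-treatment days | Change from run-in |
|---|---|---|---|---|
| Day 4 7am | 3pm Day 4 | 9/24 = 37.5% | 2–3 | 0 |
| Day 4 1pm | 9pm Day 4 | 15/24 = 62.5% | 2–3 | 0 |
| Day 4 10pm | 6AM Day 5 | 100% | 3–4 | (D4 − D2)/2 |
| Day 5 7am | 3pm Day 5 | 37.5% | 3–4 | (D4 − D2)/2 |
| Day 5 1pm | 9pm Day 5 | 62.5% | 3–4 | (D4 − D2)/2 |
| Day 5 10pm | 6AM Day 6 | 100% | 4–5 | no run-in day |
| Day 8 1pm | 9pm Day 8 | 62.5% | 6–7 | no run-in day |
| Day 8 10pm | 6AM Day 9 | 100% | 7–8 | no run-in day |

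The middle result is (D3 + D4)/2 − (D2 + D3)/2 = (D4 − D2)/2. The ±60 minutes changes no row. Five of the 15 slots bring in at least one run-in day and two bring in only run-in days. These are counts of slots, not probabilities.

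**If only about 36 h of pre-treatment CGM exist (Protocol 3.1).** Recording then starts about 7pm on Day 2 and the 24-hour run-in is Day 3 alone. The first two slots use Day 3 for both terms, so the change is still 0. The next three give (D3 + D4)/2 − D3 = (D4 − D3)/2.

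**If the 80% refers only to the part before the cut-off.** A partial Day 4 then qualifies, so a last dose at any of the three Day 4 times gives Days 3–4. One run-in day still counts as treatment, in 3 of 15 slots.

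**If the last dose is the scheduled one.** The cut-off is 6AM Day 9 for everyone, and coverage depends on when CGM stops. 80% of 24 h is 19.2 h, and 6AM + 19.2 h = 1:12AM. CGM ending before 1:12AM in the night after Day 4 gives Days 2–3. CGM ending after that, but before 1:12AM in the night after Day 5, gives Days 3–4. Protocol 3.5 discharges withdrawn subjects from the unit, so CGM may well stop.

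**Final Day 8 dose skipped (last dose taken, full-day denominator).** The last dose is then at 12pm–2pm and the cut-off at 8pm–10pm. Coverage of Day 8 is 14/24 to 16/24 = 58.3%–66.7% for 24 hours and 0% for the night, so both parameters use Days 6–7. Daytime coverage is 14/16 to 16/16 = 87.5%–100%, so daytime keeps Days 7–8. With a partial-day denominator and a 1pm last dose, Day 8 stays as a 15-hour stretch, 6AM–9PM, without its night.

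**Weight of one period.** If the regimens are balanced, 30 × 2/3 = 20 subjects receive each active regimen, and one period carries 1/20 = 5% of a regimen mean. The randomisation plan is a separate document, so balance is an assumption.

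**The case against.** A fair defence has four parts.

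*The lower bound is implied.* SAP 2.8.1 places run-in days before dosing and describes the active mean as the change while the subject was on active therapy. The authors plainly meant treated days. That stands as a reading of intent. But the sentence that selects the days contains no such limit, and a program written from it will select Days 2–3.

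*The last dose may be the scheduled one.* The match between 10pm + 8 h and 6AM supports this. If so, Day 8 is not lost when the final dose is held. The missing lower bound remains, because it then depends on when CGM stops.

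*The Day 8 loss is conditional.* It needs a skipped dose, the last dose read as taken and a full-day denominator, all together. A delayed dose would keep Day 8. Days 6–7 are in any case treated days, and whether the night after a skipped dose belongs in the comparison is a choice of estimand. All of this stands.

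*Direction and frequency are unknown.* A reader might infer that early stoppers in general are scored on their run-in days, or that the active effects are pulled toward zero. The documents do not support either. Only a last dose before 10pm on Day 4 gives two run-in days. The placebo-adjusted value is 0 minus that subject's placebo change, not 0, and its sign is open. A stop in the placebo period sets the subtracted term to 0 for both of that subject's active periods. A qd subject who stops after the Day 4 7am or 1pm dose has taken only dummy capsules in that period. A subject withdrawn before the placebo period has no placebo-adjusted value at all. No stop or hold rates are given, and the entry criteria (HbA1c 7.5–10.5%, fasting glucose at least 126 mg/dL) may make low readings uncommon.

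**Conclusion.** The point holds as a gap in a stated rule. SAP 2.8.1 and Protocol 8.3 let days before the first randomised dose count as on-treatment under each reading examined; the readings differ only in which stopping points are affected. On the literal reading, two dose slots give a change of 0 by construction and three more mix one run-in day with Day 4.

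The Day 8 loss is a second, conditional consequence of the same movable anchor. It should not be read as certain to follow from a held dose.

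The size and direction of any bias cannot be stated. What can be said is that one affected period has about 5% weight in a regimen mean, assuming 20 subjects per active regimen, and that in the skipped-dose case the window would be chosen by glucose itself. The study is stated not to be powered for significance, but its primary summary still needs a window that is fixed in advance.

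**What to change.** In SAP 2.8.1 and Protocol 8.3:

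- Take the on-treatment days as the last two qualifying 6AM–6AM days among Days 4–8 of the period, with Day 8 ending at 6AM on Day 9. Anchor this to the scheduled calendar, not to doses taken.
- Allow no day before the first randomised dose of that period.
- Define the 80% as a share of the full interval (24 h, 16 h or 8 h).
- Start follow-up at 6AM on Day 9.
- Treat a period with no qualifying day from Day 4 on as missing, and report the number by regimen. Say that the last-observation-carried-forward wording in SAP 2.2 does not fill it.
- Flag periods with stopped or skipped doses, and repeat the analysis without them.

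Both the lower bound and the calendar anchor are needed. With the cut-off still set by the last dose taken, the lower bound alone makes the first two slots missing and leaves Day 4 alone for the next three, but it does not bring Day 8 back after a skipped final dose. The calendar anchor does, giving Days 7–8 when CGM continues.

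Separately, the pre-dose CGM condition in Protocol 5.3.1.2 and the dosing schedule in Protocol 3.6 should be reconciled, so that it is clear how a held dose is recorded.

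The cost is wording only. The downside is that a few very early stoppers become missing for that period, and days after a skipped or stopped dose count as on-treatment. The flagged sensitivity analysis shows how much that matters.

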- Replace the CGM cannula at approximately 7pm (\pm 60 minutes), such that it does not interfere with any post-dose PD blood draws;
- Adverse events will be monitored and recorded.

3.3.1.4 Day 4

- Review of medications and supplements;
- Measurement of vital signs (weight, seated SBP/DPB, and heart rate);
- Randomization
- Provide a dose of study treatment or placebo at approximately 7am (\pm 60 minutes);
- Provide breakfast no sooner than 45 minutes after the morning dose;
- Provide a dose of study treatment or placebo at approximately 1pm (\pm 60 minutes), at least 45 minutes prior to lunch;
- Provide lunch no sooner than 45 minutes after the afternoon dose;
- Provide dinner at approximately 7pm (\pm 60 minutes);
- Provide a dose of study treatment or placebo at approximately 10pm (\pm 60 minutes);
- Continue CGM monitoring;
- Adverse events will be monitored and recorded.

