1.3.2 Secondary Objectives

Secondary objectives are:

- To compare pre-treatment (Day 3) to end of treatment (Day 8) mean daytime CGM glucose for single and multiple doses of ORMD-0801 vs placebo.
- To compare pre-treatment (Day 3) to end of treatment (Day 8) mean nighttime CGM glucose for single and multiple doses of ORMD-0801 vs placebo.
- To compare pre-treatment (Day 3) to post-treatment washout (Day 9) 24-hour CGM glucose for single and multiple doses of ORMD-0801 vs placebo.
- To compare post-prandial glucose measurements for single and multiple doses of ORMD-0801 vs placebo.

- To compare pre-treatment (Day 3) to end of treatment (Day 8) insulin pharmacokinetics (PK) for single and multiple doses of ORMD-0801 vs placebo.
- To compare pre-treatment (Day 3) to end of treatment (Day 8) C-peptide pharmacodynamics (PD) for single and multiple doses of ORMD-0801 vs placebo.
- To compare defined events of hypoglycemia for single and multiple doses of ORMD-0801 vs placebo.

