2.8.2. Pharmacokinetic / Pharmacodynamic Evaluations

Since Insulin is present in the subjects regardless of treatment, standard PK derivations do not apply.

The PK/PD measurements are taken pre-treatment (Day 3) and at end of treatment (Day 8). On Day 3, all subjects received Placebo, so these measurements will be used as the within subject control.

Time matched changes between Day 8 and Day 3 will be derived for the PK and PD parameters for each subject.

The following time intervals will be summarized: 0 to 60 minutes, 60 to 120 minutes, 120 to 180 minutes, 180 to 240 minutes, 240 to 300 minutes, 120 to 300 minutes and 180 to 300 minutes. Please note that the 0 to 60 minute interval will not be summarized, since it is believed that the study drug takes 60 minutes to metabolize.

The following parameters will be derived for Insulin C-Peptide for each subject:

- Positive Area (Area above 0),
- Negative Area (Area below 0),
- Absolute Area (Positive Area + the absolute value of the Negative Area),
- Maximum Difference,
- Time of Maximum Difference,
- Positive Area / hr (for the 120 to 300 minutes and 180 to 300 minutes intervals only),
- Negative Area / hr (for the 120 to 300 minutes and 180 to 300 minutes intervals only), and
- Absolute Area / hr (for the 120 to 300 minutes and 180 to 300 minutes intervals only).

The Positive Areas, Negative Areas and Absolute Areas will be compared using a one-way analysis of variance (ANOVA) with Fisher's LSD being used for pairwise treatment group comparisons.

The maximum difference and time of maximum difference will be compared in a pairwise fashion using the Wilcoxon Rank Sum test.

The PK/PD analysis will be conducted using model-independent methods and will be based on plasma concentrations of insulin and C-peptide. Individual plasma concentrations of insulin and C-peptide will be listed for each subject and sampling time and summarized descriptively using the arithmetic mean, SD, CV (%), median, minimum and maximum. Individual plasma concentration-time profiles of insulin and C-peptide will be plotted on both a linear and a semi-logarithmic scale. Mean values will also be presented graphically.

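### Post-prandial glucose against placebo is a secondary objective, but SAP 2.8.1 plans no baseline-adjusted, within-subject estimate of it

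*SAP*

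**What the plan says.** The objective is worded identically in Protocol 2.2 and SAP 1.3.2: "To compare post-prandial glucose measurements for single and multiple doses of ORMD-0801 vs placebo".

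SAP 2.8.1 gives the window, "post-prandial (first hour after meal start time including breakfast, lunch, and dinner", and lists it beside the 24-hour, daytime and nighttime values as something to be summarised. The output is stated as "The mean, standard deviation, minimum, maximum, first quartile, median, third quartile and inner-quartile range will be presented".

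The next paragraph of SAP 2.8.1 turns to derived quantities. There the AUC "will be derived for each of the time periods (24-hour, daytime and nighttime) using the indicated days". The average glucose is the AUC divided by observed hours. The change from run-in, the placebo-adjusted change and the ANOVA follow from that average. Post-prandial glucose is not in the list.

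Protocol 8.3 names the same three periods and does not mention post-prandial glucose. The planned post-prandial outputs are Listing 16.2.6.5 and Table 14.2.4.1.

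**The concern.** The trial is a crossover with a placebo run-in before each treatment period. Its strength is that each subject supplies both a run-in baseline and a placebo period for comparison. SAP 2.8.1 uses both for three CGM periods and neither for the post-prandial one, although the objective is worded as a comparison with placebo in the same way.

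What is left is a side-by-side reading of by-group descriptive statistics. In this design the groups are overlapping but different sets of subjects, and the run-in baseline is not used. An objective to compare that has no specified contrast also leaves the choice of contrast open until the data have been seen.

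**Working it through.** The plan has no figure to reproduce: the sample size of 30 is given without inputs, and both documents say that the study is not powered. The check sets the sections side by side and adds simple counting.

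**1. Which periods reach the placebo contrast (SAP 2.8.1)**

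| Period | Descriptive summary | AUC and average | Change from run-in | Placebo-adjusted change and ANOVA |
|---|---|---|---|---|
| 24-hour | yes | yes | yes | yes |
| Daytime | yes | yes | yes | yes |
| Nighttime | yes | yes | yes | yes |
| Post-prandial | yes | not listed | no input | no input |

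The steps form a chain. For subject i on regimen r:

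- average = AUC / observed hours
- change(i, r) = average on treatment days − average on run-in days
- D(i, r) = change(i, r) − change(i, placebo)

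Without a post-prandial average, the later steps have nothing to work on.

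**2. Who is in each column of a by-group summary**

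Inputs: about 30 subjects, each receiving placebo and two of the three active regimens (Protocol 3.1 and 5.2). Balanced allocation is an assumption, because the randomization plan is a separate document.

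- Active subject-periods: 30 × 2 = 60
- Subjects per active regimen: 60 / 3 = 20
- Subjects in the placebo column who never took a given regimen: 30 − 20 = 10
- Subjects shared by any two active columns: 20 + 20 − 30 = 10

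The column means therefore mix treatment differences with differences between subjects. The standard deviation of D also cannot be recovered from the columns. With s_A and s_P the standard deviations of the active and placebo changes, Var(D) = s_A² + s_P² − 2ρ·s_A·s_P. A by-group summary does not report the within-subject correlation ρ.

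**3. What the existing ANOVA tests**

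Its purpose is stated as "to determine whether multiple doses a day has an effect on the CGM parameters". Its response is already D, so its treatment levels are qd, bid and tid, and its null hypothesis is mean D(qd) = mean D(bid) = mean D(tid). That can hold whether the common value is zero or not. The comparison with placebo is the separate question of whether mean D(r) is zero for each regimen. Adding post-prandial glucose to the ANOVA alone would not answer it.

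**4. Timing of the one-hour window (side note)**

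The SAP leaves out the first 60 minutes after dosing in its insulin and C-peptide section because "it is believed that the study drug takes 60 minutes to metabolize". Breakfast and lunch come at least 45 minutes after the dose. For a gap of g minutes, the window runs from g to g + 60 minutes after the dose, and max(0, 60 − g) minutes fall before the 60-minute mark.

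| Gap g | Minutes before the 60-minute mark |
|---|---|
| 45 | 15 of 60 |
| 50 | 10 of 60 |
| 55 | 5 of 60 |
| 60 or more | 0 |

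This can arise in only 3 of the 9 regimen-meal pairs: bid breakfast, tid breakfast and tid lunch. In the other six, the latest active dose is at least 240 minutes before the meal. Over three meals the maximum is 0/180 for qd, 15/180 (8.3%) for bid and 30/180 (16.7%) for tid.

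**The case against.** The best defence is that a comparison is planned, only descriptively. SAP 2.1 requires summaries by study group, with 95% confidence intervals where appropriate, and every subject receives placebo. The hypoglycemia objective is also worded as a comparison, and SAP 2.7.2 meets it with percentages and event rates by treatment. The table shells are in a separate file, and the primary Table 14.2.1.1 is also titled as a summary, so the title of Table 14.2.4.1 does not settle its content. The study is not powered.

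Much of this stands. A reader might infer that the plan never sets post-prandial glucose against placebo, or cannot address the objective. The documents do not support that: by-group summaries are planned. The defence does not explain why three CGM periods in the same unpowered study get the within-subject derivation and the fourth does not. Nor does the undefined term for CGM parameters in the ANOVA sentence fill the gap, since no post-prandial change is derived to feed it.

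Two other stronger readings are tempting.

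- **The first-hour window largely misses the drug's action.** The overlap in step 4 needs a meal less than 60 minutes after an active dose, and 45 minutes is a minimum, not the scheduled gap. At the worst, 45 of the 60 minutes lie after the mark. Expressing the window as a share of 60 to 300 minutes after the dose is not supported either: the SAP never calls that the active period, and 300 minutes is simply where blood sampling stops (Protocol 6.5). Reading the 60-minute statement as the onset of a glucose effect is itself an inference.
- **The Day 3 cannula change spoils the baseline dinner.** The instruction is "Replace the CGM cannula at approximately 7pm", close to dinner. Both have a window of ±60 minutes, the change is scheduled alike in all three periods, and no length of signal loss is given. The run-in rule takes the last two days with at least 80% of expected measurements, not Day 3 alone.

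**Conclusion.** The concern holds for the missing contrast. SAP 2.8.1 gives a secondary objective against placebo descriptive statistics only, and plans no estimate that uses the run-in baseline and the within-subject pairing. The by-group summaries that remain compare overlapping but different subjects: about 20 per active regimen against about 30 on placebo, if allocation is balanced.

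The consequence is a less informative and less clearly specified analysis of one secondary objective. It is not the loss of a powered test, and the 24-hour, daytime and nighttime analyses are unaffected.

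The timing of the window is worth at most a note: for bid breakfast, tid breakfast and tid lunch, up to 15 of the 60 minutes can fall before the SAP's 60-minute mark if the meal starts at the 45-minute minimum. It does not justify a different window, and the cannula change does not justify excluding the Day 3 dinner.

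**What to change.** In SAP 2.8.1, add post-prandial glucose, per meal and pooled over meals, to the periods for which the average, the change from run-in and the placebo-adjusted change are derived. Keep the first-hour definition.

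For each active regimen, report the mean placebo-adjusted change with a 95% CI. For a given measure and regimen each subject contributes one value, so a one-sample interval is enough. The ANOVA may be kept for the comparison among active regimens, but it should not be presented as the placebo comparison. Add these results to Table 14.2.4.1.

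The cost is SAP wording and one more set of values derived from CGM data already collected, with no change to any subject procedure. The downside is one more unpowered secondary comparison. Naming the pooled value as the main post-prandial result and the per-meal values as supportive would keep it to one. If the sponsor prefers not to add the contrast, the SAP should say that this objective will be described only; that is the weaker option.
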